8.1.3. Primary Endpoint Assessments (Visit 3, Study Day 60)

Patients will come to the study clinic for Primary Endpoint Assessments at Study Day 60.

The following assessments will be completed:

- Review of patient information relevant to XADAGO administration and concomitant medications administration
- Assessment of AEs
- Review of PRO completion compliance
- Clinical outcome assessments administered by the PI/certified HCP designee:
 - MDS-UPDRS
 - MoCA
 - CGI-C
- PRO assessments:
 - PDQ-39
 - TSQM-9
 - PGI-C

8.1.4. Follow-Up Study Assessments (Visit 4 [Study Day 90], Visit 6 [Study Day 180])

Patients will come to the study clinic on Study Days 90 and 180.

The following assessments will be completed:

- Review of patient information relevant to XADAGO administration and concomitant medications administration
- Assessment of AEs
- Review of PRO completion compliance
- Clinical outcome assessments administered by the PI/certified HCP designee:
 - MDS-UPDRS
 - MoCA (Visit 6 only)
 - CGI-C
- PRO assessments:
 - PDQ-39
 - TSQM-9
 - PGI-C

8.1.5. PRO Assessment Timepoints (Visit 5 |Study Day 120|)

PRO assessment:

- TSQM-9

8.2. Number of Patients

Up to 600 patients are planned for screening. This is expected to result in a final sample size of up to 540 eligible and evaluable enrolled patients, distributed among approximately 50 investigative sites in the US.

Table 3: Schedule of Assessments

Protocol Activity (Visit Type, Location, and Number; Study Day and Month; Window Allowance)	2-Month Main Study			4-Month Extension Study		
	Screening/Baseline Assessment Visit ^a	Follow-up	Primary Endpoint Visit	Follow-up	PRO Assessment Only	Follow-up
	Clinic	Telephone	Clinic	Clinic		Clinic
	Visit 1	Visit 2	Visit 3	Visit 4	Visit 5	Visit 6
	Day 1	Day 30	Day 60	Day 90	Day 120	Day 180
	Month 1		Month 2	Month 3	Month 4	Month 6
	±7 days	±2 days	±7 days	±7 days	±7 days	±14days
Informed Consent and HIPAA Authorization	X					
Eligibility: Inclusion/Exclusion Criteria	X					
Medical History and Demographics	X					
Medical History of PD, other Neurological Conditions	X					
Presentation of Study Instructions to Patient	X					
Registration and Training on eCOA System	X					
Concomitant Medications Assessment ^b	X	X	X	X		X
XADAGO Administration Compliance Review ^b		X	X	X		X
PRO Compliance Review ^b			X	X		X
Adverse Events Assessment ^b			X	X		X
MDS-UPDRS ^b	X		X	X		X
PDQ-39 ^c	X		X	X		X
MoCA ^b	X		X			X
TSQM-9 ^c		X	X	X	X	X
CGI-C ^b			X	X		X
PGI-C ^c			X	X		X

^a Screening will take place not more than 7 days before the Baseline Visit and may occur at the same time as the Baseline Visit. The first study dose of XADAGO will occur in the clinic on the Baseline Visit day, which will be designated Study Day 1.

^b Assessments to be administered by the PI/certified or HCP designee.

^c Assessments to be completed by the patient, with Care Partner assistance, if required.

8.3. Criteria for Study Termination

US WorldMeds, LLC (USWM), the study Sponsor, has the right to terminate this study at any time. The PI will be notified by telephone and/or in writing if the Sponsor decides to suspend or discontinue the study for any reason. The written notice will provide the PI with the reason that the study was suspended or discontinued along with instructions on how the site should proceed to close down the study.

Reasons for terminating the study may include, but are not limited to, the following:

- Discovery (from this or other studies) of an unexpected, serious, or unacceptable health hazard to patients
- A decision on the part of the Sponsor to suspend evaluation or marketing of the product
- Unsatisfactory patient enrollment
- Failure of the PI and/or investigative site to comply with pertinent FDA regulations
- Insufficient adherence to protocol requirements or an unacceptably high rate of missing, erroneous, or improperly collected data that threatens the scientific integrity of the study
- Evidence from the data that there are sufficient technical problems with the study to believe with a high degree of certainty that patients are being involved in the study without a realistic expectation of evaluable data

9. SELECTION AND WITHDRAWAL OF PATIENTS

9.1. Inclusion Criteria

1. Patient (and Care Partner if required per Inclusion 7) is able to understand and provide signed informed consent and HIPAA authorization in English
2. Diagnosis of idiopathic PD (all stages)
3. Male or female, 30 to 80 years of age, inclusive, at initial screening assessment
4. Independent of the study, clinician's and patient's choice of treatment is XADAGO in accordance with the Package Insert indication ([Appendix A](#))
5. Patient is willing and able to participate in the study and complete study-related assessments for 2 months and, patients can continue for an optional 4-month study extension
6. Patient has access to an electronic device for the interim completion of PROs
7. Patient has an available Care Partner who is able and willing to assist with clinic attendance and completion of study assessments (e.g., PROs, health outcomes, etc.), if in the PI's opinion, assistance is needed to comply with all study visits and procedures

9.2. Exclusion Criteria

1. Any of the warnings, precautions, or contraindications listed in the Package Insert ([Appendix A](#)) that in the opinion of the PI would prevent appropriate treatment with XADAGO or impair study participation (e.g., pregnancy, lactation, severe hepatic impairment, etc.)
2. Participation in any other clinical trial of an investigational drug or device within 4 weeks prior to the Baseline Visit or at any time during this study
3. Patient is currently receiving chemotherapy or radiation for any form of cancer (if history of cancer, must be in clinical remission at study entry) or currently receiving immunotherapy
4. Patients with conditions that are likely to prevent them from accurately and reliably completing study assessments, including evidence of moderate or severe dementia as determined by the clinician (not to include mild cognitive impairment [MCI]); major psychiatric illness (specifically diagnosis of schizophrenia, bipolar disorder or a history of attempted suicide); and/or severe and progressive medical illness (including terminal cancer, end-stage renal disease +/- undergoing dialysis)
5. Severe or unpredictable dyskinesia at the time of the Baseline Visit
6. Previous participation in this study; a patient may not re-enroll after prior discontinuation or completion

9.3. Screening or Enrollment Failures

A screening and enrollment log for all potential study participants who are assessed, and for those patients who have provided written informed consent and HIPAA authorization and

completed Baseline Assessment Visit procedures, will be maintained at the Investigator's site.

Potential study participants who fail the study inclusion/exclusion criteria may be re-assessed for inclusion at the PI's discretion at a minimum of 2 weeks later. Re-assessed potential participants must fulfill all study criteria to be considered eligible for enrollment. Per Exclusion Criterion 6, a patient who has completed the study may not enroll a second time.

9.4. Patient Withdrawal Criteria

Any patient not completing the study for any reason will be considered a premature discontinuation and the study site staff must record the reason(s) for withdrawal in the patient's study records. Patients who discontinue or are withdrawn from the study may not re-enter the study.

A patient is free to withdraw consent from the study at any time, regardless of his/her reasons, and without prejudice against further treatment. The patient (and Care Partner, if applicable) will be queried about the reason(s) for the decision to withdraw consent and the reasons(s) must be clearly documented in the patient's study record to ensure the decision was not due to an AE. If withdrawal was due to an AE, including SAE, the AE should be indicated as the reason for discontinuation even if the PI would not have considered discontinuation from the study because of the AE.

The PI or Sponsor may withdraw an individual patient from the study at any time if it is deemed clinically appropriate. Circumstances can include the following:

- Patient's safety may be compromised due to intolerable AEs or a physical or mental condition
- Patient requires a medication that was prohibited on this study
- Patient is non-compliant with required study regimens or procedures specified in this protocol
- Patient is lost to follow-up

Any patient who experiences an SAE or is removed from the study because of an intolerable AE must be followed until the event resolves or stabilizes. If a patient cannot be reached for the telephone follow-up contacts or fails to return for any study visits required by the PI, repeated attempts will be made to reach the patient (or Care Partner, if applicable) (defined as a minimum of 3 telephone calls, followed by sending a certified letter). If repeated attempts are unsuccessful, lost to follow-up will be recorded in the patient's study record. The PI should always inform a patient that he/she has been withdrawn from participation in a study and the reasons for withdrawal.

10. XADAGO AND OTHER MEDICATIONS

10.1. XADAGO

XADAGO is an FDA-approved and marketed product in the US. The Sponsor will initially provide to each qualified and activated site a supply of XADAGO (described in Section 10.1.1) only for use in the study. Kits will be uniquely labeled for tracking kit assignments to each study patient.

When a patient is prescribed XADAGO and the patient agrees to participate in the study, which includes providing informed consent, the patient will be considered an enrolled study patient.

Patients who discontinue XADAGO treatment during the conduct of the study can remain in the study or discontinue early (Section 10.1.4).

10.1.1. XADAGO Study Supplies

Each site will receive a supply of XADAGO to begin the study:

- 3 patient kits, each of which will contain:
 - 1 blister pack of 50-mg tablets
 - 4 blister packs of 100-mg tablets
- 2 extra blister packs of 50-mg tablets
- 3 bags

10.1.2. XADAGO Drug Storage

XADAGO should be stored at 25°C (77°F) with excursions between 15°C to 30°C (59°F to 86°F) permitted per [Appendix A](#) (Package Insert).

10.1.3. XADAGO Accountability**10.1.3.1. Site Accountability**

Accurate recording of all XADAGO study supplies received by the site and dispensed to patients in a XADAGO Study Kit will be maintained by study site personnel.

At the end of the study, all unused XADAGO supplies or XADAGO Study Kits returned by study participants should be inventoried. If any XADAGO Study Kit is lost or damaged, its disposition should be documented. The Sponsor will provide instructions to return the unused study kits to the Sponsor's designee at the end of the study.

10.1.3.2. Patient/Care Partner Accountability

Patients will take XADAGO as directed by the treating physician. Patients/Care Partners will be responsible for obtaining and storing XADAGO medication taken during the study and informing site study staff of any changes.

10.1.4. XADAGO Discontinuation

If an enrolled patient discontinues XADAGO treatment for any reason at any point in the study, the patient is permitted to remain on study and complete the full schedule of assessments per protocol, as long as the patient is otherwise eligible, and is able and willing to continue study participation through the end of the Main Study or the Extension Study, as appropriate. Refer to Section 9.4 for patients who discontinue XADAGO and wish to discontinue the study.

10.2. Parkinson's Disease Medications and Other Medications

Patients will continue taking all prescribed PD medications (e.g., levodopa / carbidopa) including any other prescribed medication as directed by the treating physician. Any changes to prescribed regimen should be reported to study clinic staff.

11. SAFETY MANAGEMENT

11.1. Safety Assessments

The use of XADAGO in this study is not experimental, study procedures are not greater than minimal risk, and safety is not the principal objective of this protocol. In keeping with the Sponsor's requirement, however, to review and report all information relevant to the safety of the marketed drug, XADAGO, about which the Sponsor becomes aware through notification by the investigator and study patients, all AEs spontaneously reported by the patient and/or in response to an open question from the site study personnel or revealed by observation will be recorded at the investigational site for each study patient during his/her active participation in the study.

Additional information regarding AE reporting is available from the following sections of the CFR from the FDA, as well as from the designated website: CFR: §314.80, <http://www.fda.gov/medwatch/index.html>.

Please note that the governing Institutional Review Board (IRB) may impose additional safety reporting requirements with which the investigator's site must comply.

11.2. Definition of Adverse Events

11.2.1. Adverse Event (AE)

An AE is the development of an undesirable medical condition or the deterioration of a pre-existing medical condition following or during exposure to a pharmaceutical product, whether or not considered related to the product.

11.2.2. Serious Adverse Event (SAE)

A serious adverse event is an AE occurring at any dose that results in any of the following outcomes:

- Death
- Life-threatening
- Patient hospitalization or prolongation of existing hospitalization
- Persistent or significant disability/incapacity
- Congenital anomaly or birth defect
- Important medical event that, based upon appropriate medical judgment, may jeopardize the patient or require medical or surgical intervention to prevent one of the outcomes listed above

11.3. Relationship to XADAGO

For each AE, the investigator will assess the attribution of XADAGO to the AE and determine whether the AE is or is not related to XADAGO as defined below. When in doubt, the AE should be considered at least "possibly related" until further evidence becomes available to refute this assessment.

- Definitely Not Related
 - Patient did not receive XADAGO, the temporal sequence of the AE onset relative to administration of XADAGO is not reasonable, or there is another obvious cause of the AE.
- Possibly Related
 - There is evidence of exposure to XADAGO and the temporal sequence of the AE onset relative to administration of XADAGO is reasonable, but the AE could have been due to another equally likely cause.
- Probably Related
 - There is evidence of exposure to XADAGO, the temporal sequence of the AE onset relative to administration of XADAGO is reasonable, and the AE is more likely explained by taking XADAGO than by any other cause.
- Definitely Related
 - There is evidence of exposure to XADAGO, the temporal sequence of the AE onset relative to administration of XADAGO is reasonable, the AE is more likely explained by taking XADAGO than by any other cause, and the AE shows a pattern consistent with previous knowledge in the label of XADAGO or similar drug class.

AEs determined by the investigator to be “possibly” or “probably” related will be documented as related to XADAGO for the purposes of expedited regulatory reporting and clinical reporting.

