11.4.2. Serious Adverse Event (SAE)

All SAEs (related and unrelated) that occur for any patient after signing an informed consent for this study and having taken XADAGO must be recorded by the investigator and reported. The site should record the SAE in the patient's source medical record within 24 hours of observation or notification that such an event has occurred. The patient's medical record should be completed with as much information as is available at that time with the knowledge that full clinical details may not be immediately available. The Sponsor will contact the site if additional information is required regarding the SAE. In addition, an SAE form located in the ISF binder must be completed and submitted to (see [Table 1](#) for details).

All SAEs must be followed until they resolve or stabilize (i.e., a new baseline has been established). The PI must provide the Sponsor with all relevant follow-up information necessary to facilitate a thorough understanding of the experience and judgment regarding the relationship to XADAGO. Patients who discontinue because of an SAE before study completion will be contacted 7 days (± 3 days) after discontinuation to determine if the SAE has resolved, continues unabated, or has reached a new baseline.

Reports of congenital abnormalities/birth defects are SAEs. Spontaneous miscarriages should also be reported and handled as SAEs. Elective abortions without complications should not be handled as AEs.

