### **9.1. Overall Summary of Tolerability**

The overall summary of tolerability table presents the data for all treated subjects by cohort and overall. Entries in this table are the number of:

1. Subjects treated and subject months of drug exposure by treatment (50 mg vs 100 mg).
2. Subjects with adverse events.
3. Adverse events.
4. Subjects with serious adverse events.
5. Subjects discontinuing due to adverse events.
6. Deaths.

The subject data listing provides a complete disclosure of adverse events as recorded in the CRF and supports this table and all other AE summary table subsets.

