#### **9.2.1. Summaries of Adverse Event Incidence Rates for All Subjects**

The primary presentation of AEs data is prepared without regard to causality or relationship to study medication and classifies events using the most recently available MedDRA dictionary with respect to preferred term and body/organ system for all treated subjects by cohort and overall. Subjects will be counted only once at the body system level and will be counted once for each applicable preferred term; multiple occurrences of the same preferred term for a subject will be counted only once. Subjects who experience more than one event within the same body system are counted once at each preferred term level.

Supplementary tables summarize the events with respect to the maximum severity observed for each preferred term and highest relationship to study medication by cohort and overall. The presentation of adverse events with respect to the severity or intensity of the event usually categorizes the data as mild, moderate, or severe.

The relationship of the event to study medication will be collapsed into two categories, related and not related:

1. Related combines the options possible, probable, and highly probable.
2. Not related is a combination of unlikely and not related.

A by-subject listing of serious adverse event data will be presented.

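### Protocol 11.3's documented-as-related sentence leaves out 'Definitely Related', and SAP 9.2.1 groups causality by labels that differ from the protocol's four ratings

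*Protocol*

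**What the plan says.** Protocol 11.3 asks the investigator to "determine whether the AE is or is not related to XADAGO as defined below" and then defines four ratings: Definitely Not Related, Possibly Related, Probably Related and Definitely Related. The section ends with the rule that turns a rating into a classification for expedited regulatory reporting and clinical reporting: "AEs determined by the investigator to be “possibly” or “probably” related will be documented as related to XADAGO". That sentence does not mention 'Definitely Related'.

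SAP 9.2.1 reduces causality to two groups with its own labels: "Related combines the options possible, probable, and highly probable" and "Not related is a combination of unlikely and not related". The grouping concerns the tables described just before it, which are produced for each cohort and for all patients together: "Supplementary tables summarize the events with respect to the maximum severity observed for each preferred term and highest relationship to study medication".

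Three other statements limit the reach of the point:

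- SAP 9.2.1, on the main AE table: "The primary presentation of AEs data is prepared without regard to causality or relationship to study medication".
- Protocol 11.4.2 requires sites to record and report SAEs whatever their cause: "All SAEs (related and unrelated) that occur for any patient after signing an informed consent".
- SAP 9.1, on the listing: "The subject data listing provides a complete disclosure of adverse events as recorded in the CRF".

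**The concern.** Both rules work by naming the ratings that belong to the related group, and neither names 'Definitely Related'. The SAP also uses two labels, 'highly probable' and 'unlikely', that the protocol does not define. No section available for review links the two scales.

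A programmer who followed the SAP text to the letter would have no instruction for an event recorded as 'Definitely Related'. The documents do not say what happens to a value that is in neither group. The 'highest relationship' rule makes the gap sharper. If one patient has the same preferred term once as Possibly and once as Definitely Related, the rating that should decide the cell is the one with no listed group.

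What is at stake is the consistency of the related/not-related split in the supplementary table, and the wording of the protocol rule for reporting.

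**Working it through.** No sample size, error rate or other plan figure is involved. The check sets the two scales side by side.

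**Inputs.** The four ratings and the documented-as-related sentence come from Protocol 11.3. The five labels and two groups come from SAP 9.2.1.

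| Protocol rating | Named in Protocol 11.3 sentence | SAP label by name | SAP label in substance | SAP label by rank only |
|---|---|---|---|---|
| Definitely Not Related | no, as expected | none | not related | not related |
| Possibly Related | yes | possible | possible | possible |
| Probably Related | yes | probable | probable | probable |
| Definitely Related | **no** | **none** | **none stated** | highly probable |

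**Step 1, protocol rule.** Three ratings contain 'Related' without 'Not'. The sentence names two of them, so 3 − 2 = 1 is left out, and it is the strongest.

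**Step 2, protocol to SAP.** The count of matched ratings depends on the criterion:

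- By name, allowing possibly/possible and probably/probable: 2 of 4.
- Also taking 'Definitely Not Related' as 'not related' in substance: 3 of 4.
- By rank, which also pairs the top related level of each scale: 4 of 4. This pairing is an inference and is not written in either document.

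**Step 3, SAP to protocol.** Two of the five SAP labels, 'highly probable' and 'unlikely', are not protocol ratings. Pairing by rank accounts for 'highly probable' but still leaves 'unlikely' without a protocol rating.

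**Step 4, intent.** Protocol 11.3 gives three criteria for Probably Related: exposure, reasonable timing, and XADAGO as the more likely explanation. Definitely Related requires the same three plus a known pattern, so four. Any event that meets the definition of Definitely also meets every criterion of Probably. The intent that it counts as related is therefore not in doubt, and the fault lies in the written rule.

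**Step 5, dependence on the eCRF.** The causality options in the eCRF are not shown, so there are two cases:

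- The eCRF offers the protocol's four ratings. Then 'Definitely Related' can be recorded and SAP 9.2.1 does not place it. The labels 'highly probable' and 'unlikely' are simply unused, and under SAP 6.1 rows generally appear only where data exist.
- The eCRF offers the SAP's five labels. Then SAP 9.2.1 covers every recorded value and there is no gap in the analysis rule. The remaining fault is that investigators would be choosing among labels of which the protocol does not define two.

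The documents need aligning in either case, but an unplaced value arises in the table only in the first.

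**The case against.** The strongest reply is that nothing is really excluded. The protocol asks for a related/not-related determination, and a rating called 'Definitely Related' answers that by its name. The closing sentence can be read as settling only the uncertain ratings, which would explain why 'Definitely Not Related' is absent too. It also fits the instruction in the same section to treat doubtful cases as at least possibly related. On the SAP side, 'options' may refer to the actual eCRF choices, and the eCRF, the site-file instructions mentioned in Protocol 11.4.1 or the table shells mentioned in SAP 6.4 may supply the link.

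Much of this stands. The intent is clear, and the analysis gap depends on material that is not shown. What does not fall away is that both rules list ratings by name and the list is incomplete, and that the two scales differ in structure. SAP 6.2 requires decodes in the table notes, so the handling should be visible, but disclosure afterwards is not prespecification.

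A reader might infer that definitely related events will be reported as unrelated, or that related-AE counts will be too low. The documents do not support either inference. They nowhere assign the rating to the not-related group, and they do not say whether an unlisted value would be set to related, shown separately, queried or left missing.

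**Conclusion.** The point holds as a minor inconsistency in wording, within the protocol and between protocol and SAP. Read literally, the strongest causality rating is outside the related group in both rules. This is certain for the wording. Whether it touches the analysis depends on the eCRF options: it can if the eCRF uses the protocol's four ratings, and it does not if it uses the SAP's five labels.

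The reach is limited to the protocol's relatedness classification and the SAP's supplementary relationship table. The primary AE table, site reporting of all SAEs and the AE listing do not depend on the grouping. The effect on the number of related AEs cannot be derived, because the documents do not show how often the rating will be used or how an unlisted value will be handled. It may be nil.

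**What to change.** First check the causality options in the eCRF. Then, before the database freeze that SAP 2 sets as the limit for analysis decisions, make one of two edits to SAP 9.2.1:

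- If the eCRF uses the protocol's ratings: Related = Possibly, Probably or Definitely Related; Not related = Definitely Not Related. This places 4 of 4 ratings and leaves no undefined label.
- If the eCRF uses the SAP's five labels: keep the two groups and state how each label maps to the protocol's four ratings.

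Either edit is a few lines and needs no new data.

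At the next protocol amendment, add 'definitely' to the documented-as-related sentence in Protocol 11.3. The wording change is one word, but Protocol 14.2 requires each investigator to obtain IRB approval before an amendment is implemented. That applies across approximately 50 sites by Protocol 8.2, or approximately 30 by SAP 4.3.1. With either number it is not worth an amendment of its own, and the SAP edit is enough for the analysis.
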